Identifiers: NCT03453164 Unique Protocol ID: RK29040

Brief Title: Checkpoint Inhibitor and Radiotherapy for Recurrent Gastric Cancer (CIRCUIT)

Date: 20 Sep, 2017

Phase I/II Clinical Trial of Nivolumab (Anti-PD-1 Antibody)

in Combination with Local Radiation Therapy

for Unresectable Advanced or Recurrent Gastric Cancer

Refractory to Standard Therapy

CIRCUIT trial

Principal Investigator: [name]

Gastrointestinal Tract Surgery, Fukushima Medical University Hospital

[name]

[contact] ([name])

E-mail: [contact]

Research Plan Summary

Purpose of Research

Patients with unresectable advanced or recurrent gastric cancer with intolerance or progression for standard treatment (primary and secondary chemotherapy) will receive short-term radiation therapy on selected lesions prior to nivolumab (anti-PD-1 antibody) therapy, which is approved as a third-line chemotherapy, to determine its safety and efficacy (enhancement of the systemic effect of nivolumab and sensitization of the local effect of radiation).

Method of Research

Candidates: Patients with unresectable advanced or recurrent gastric cancer who are diagnosed as ineffective (intolerant or progression) to standard treatment (first-line or second-line chemotherapy) and have two or more lesions that can be confirmed by imaging.

Preliminary review, confirmation of eligibility criteria, acquisition of consent to participate in this study, registration

Treatment = Radiotherapy + Nivolumab (anti-PD-1 mAb)

- ① **Radiotherapy:** If the patient has symptoms such as pain or paralysis, irradiate the lesion thought to be the main cause of symptoms, or if asymptomatic, irradiate the largest lesion (or the second largest lesion if radiotherapy to the largest lesion is difficult) with 4.5 Gy once a day for 5 days (total 22.5 Gy/5 times/5 days). Day 1 is the start date of radiotherapy.
- ② **Nivolumab:** Start administration between Days 15–22. Nivolumab is administered at 3 mg/kg body weight or 240 mg every 2 weeks for a total of six doses.

Observation and Evaluation of Efficacy

Evaluation Items

Primary endpoint: 1) Disease control rate

Secondary endpoints: 1) Median survival time,

2) Safety (grade and frequency of adverse events),

3) Local control rate

4) Immunological parameters

• **Expected Number of Cases**

40 cases

Duration of Study

Registration period: March 1, 2018 to August 31, 2020 (2 years and 6 months)

1.1. Background and Significance

Treatment of unresectable advanced or recurrent gastric cancer

Chemotherapy is the first line treatment option that is considered for unresectable advanced or recurrent gastric cancer. Currently, in Japan, the combination therapy of oral fluoropyrimidine antineoplastic agents (S-1, capecitabine) plus platinum (cisplatin, oxaliplatin) is recommended as first-line treatment for HER2-negative gastric cancer, and ramucirumab plus paclitaxel as second-line treatment. Trastuzumab combination therapy is also recommended for HER2-positive gastric cancer (1). Recent advances in chemotherapy have allowed a high degree of tumor reduction in unresectable advanced or recurrent gastric cancer, but the median survival time is approximately 6–13 months based on the results of national and international clinical trials, and the prognosis is still poor.

In 2017, the results of a multicenter international clinical trial of the immune checkpoint inhibitor, nivolumab (anti-PD-1 antibody (Ab)), in unresectable advanced or recurrent gastric cancer that was refractory or intolerant to standard treatment were reported, showing a significant overall survival (OS) benefit (hazard ratio [HR]: 0.63; 95% confidence interval. [CI]: 0.50–0.78; $p < 0.0001$) and it was approved as a tertiary chemotherapy in Japan in 2017. However, even in the aforementioned report, the response rate was not as high as expected at 11.2% (95% confidence interval: 7.7–15.6), and the development of new treatments and combination therapies is urgently needed.

Radiotherapy is used for various malignant tumors throughout the body, but for advanced or recurrent gastric cancer that is not curatively resectable, especially in cases with multiple foci, treatment is only performed in symptomatic and conservative approaches based on the tolerable dose of the surrounding tissues and the therapeutic effect (radiosensitivity).

Combination therapy with radiotherapy and immune checkpoint inhibitors

Although there is no established consensus on the efficacy (additive or synergistic effect) of the combination of radiotherapy and immunotherapy, its efficacy has been reported in many basic studies, translational studies, case reports, and relatively small clinical studies in recent years. We have also reported the induction of cancer antigen-specific T lymphocytes after irradiation in patients with esophageal squamous cell carcinoma (2) and the drug-resistant/unresectable recurrent gastric cancer showing an abscopal effect in combination with immuno-cell therapy (3). The mechanism is thought that irradiation-induced cell death of cancer cells became new antigen and a tumor immune response was activated *in vivo*.

Significance of this examination

This clinical trial is designed to evaluate the additive effect to nivolumab and radiotherapy in patients

with unresectable advanced or recurrent gastric cancer who have been diagnosed to have an inadequate response (intolerance or progression: PD) to standard (first- and second-line) chemotherapy by combining radiation therapy immediately before the third-line nivolumab treatment. The trial will be positioned as a proof of concept (POC) to explore the efficacy of this therapy by conducting exploratory clinical and immunological analyses as a phase I/II study. The safety of this combination therapy will also be investigated as a secondary study. It is positioned to provide basic data on median survival time (MST) and percentage of local control for future randomized controlled trials (RCTs) of this therapy.

1.2. Objectives of the study

Eligible patients will be those with unresectable advanced or recurrent gastric cancer who have been diagnosed as having an inadequate response (intolerance or progression: PD) to standard therapy (primary or secondary chemotherapy) and who have at least two image-confirmed lesions (one of which is at least 2 cm in length). To evaluate the safety and efficacy of the combination immunotherapy by administering short-term radiotherapy on selected lesions prior to nivolumab (anti-PD-1 Ab) treatment, which is approved as a third-line chemotherapy, in eligible patients, the following items will be assessed:

- ① Primary endpoint: disease control rate
- ② Secondary endpoint:
 - 1. Median survival time (MST)
 - 2. Safety (grade and frequency of adverse events)
 - 3. Local control rate
 - 4. Immunological parameters:

Histological examination

- Analysis of the tumor microenvironment by immunostaining.

Peripheral blood test

- Analysis of peripheral blood lymphocyte subset
- Measurement of cytokines in plasma
- Analysis of regulatory T cell function
- Analysis of antigen-specific T cell function

2. Methods and duration of the study

2.1. Schema

- Patients with unresectable advanced or recurrent gastric cancer.
- Patients who are diagnosed as ineffective (intolerant or progression) to standard treatment (first-line or second-line chemotherapy) and have two or more lesions that can be confirmed by imaging.
- 40 cases

Obtaining consent to participate in the trial, checking eligibility criteria, enrolment

Treatment = radiotherapy ➤ Nivolumab (anti-PD-1 Ab)

Radiotherapy: 4.5 Gy once daily for 5 days (total 22.5 Gy/5 times/5 days) to the lesion thought to be the main cause of symptoms if there are symptoms such as pain or paralysis, or to the largest lesion if asymptomatic (second largest lesion if radiotherapy to the largest lesion is difficult). The day that radiotherapy is started is Day 1.

Nivolumab: Dosing is started between Days 15 and 22; Nivolumab is administered at 3 mg/kg (body weight) or 240 mg every 2 weeks for a total of six doses.

End of administration

Follow-up (~Day 180 ± 14) and efficacy assessment (Day 180 ± 14)

End of trial

2.2. Research design

Phase I/II, single-arm, open (non-randomized), prospective study

2.3. Treatment and intervention plans

(1) Test chemicals/test equipment

Radiation therapy X-rays or electron beams generated by radiation therapy equipment installed in the Department of Radiation Therapy at Fukushima Medical University

Hospital and the Department of Radiation Oncology at Kanagawa Cancer Center.

Nivolumab (Anti-PD-1 Ab) Ono Pharmaceutical Industries Ltd/Bristol-Myers Squibb Co.

Opdivo intravenous infusion 20 mg, 100mg

(2) Dosage/applications

Radiotherapy

Exposure 22.5 Gy/5 times/5 days

Irradiation range

In accordance with the usual treatment methods used in symptomatic and palliative treatment, only the tumor is targeted and the irradiated area has a margin that takes into account the physical uncertainties assumed at each irradiated site (i.e. the clinical and prophylactic irradiation area is not considered).

Basis for setting

Prognosis and early initiation of nivolumab therapy are priorities, and the main target lesions were assumed to be liver metastases, lymph node metastases, local (surgical) recurrent lesions and bone metastases. Therefore, the radiotherapy period was kept short and the irradiation dose was set at 22.5 Gy/5 times/5 days, which is below the tolerable dose at each site and close to the tolerable dose in the brain and spinal cord.

Selection of irradiated tumors

If symptoms such as pain or paralysis are present, the lesion thought to be the main cause of symptoms should be selected; if asymptomatic, the largest lesion (or the second largest if radiotherapy of the largest lesion is difficult) should be selected. Tumors larger than 2 cm should be selected, taking into account the possibility that tumors that are too small may not cause an adequate biological response (induction of anti-tumor immunity).

Irradiation day interval

Radiotherapy is performed on consecutive Department of Radiation Therapy working days (weekdays and consecutive days). This does not apply during the end of the year and New Year holidays, national holidays and other holidays.). The day that radiotherapy is started is Day 1. If radiotherapy is not completed by Day 14, the patient is considered to have dropped out.

Irradiation implementation conditions

On each irradiation day, ensure that all of the following conditions are met before the day's irradiation

- 1) Body temperature: < 38.5°C (axilla)
- 2) Confirmation by the attending doctor that there are no problems with radiotherapy.

If the above criteria are not met, irradiation is postponed on a day-to-day basis until the criteria are met.

Nivolumab (anti-PD-1 Ab) treatment

Dosage and administration

In accordance with the recommended treatment for unresectable advanced or recurrent gastric cancer, 3 mg/kg (body weight) of nivolumab once every two weeks over at least one hour, or 240 mg once every two weeks over at least 30 minutes, is administered via intravenous infusion.

A total of six administered doses is considered the completion of protocol treatment, but there are no specific provisions for treatment after completion.

Continuation of treatment with nivolumab is also permitted within the insurance coverage at the discretion of the attending doctor.

However, any 'unacceptable concomitant or supportive therapy' as defined in 2.4.3) shall be considered a protocol deviation.

Dosing conditions

All of the following conditions should be met when starting administration of this drug.

- 1) White blood cell count \geq 3,000/ μ L and neutrophil count \geq 1,500/ μ L
- 2) Hemoglobin \geq 9.0 g/dL
- 3) Platelets \geq 100,000/ μ L
- 4) Total bilirubin \leq 2.0 times the upper limit of the institutional reference value
- 5) AST (GOT) and ALT (GPT) \leq 3.0 times the upper limit of the facility reference value. (If liver metastases are present, \leq 5.0 times the upper limit of the institutional reference value.)
- 6) Serum creatinine \leq 1.5 times the upper limit of the facility reference value or creatinine - clearance(Ccr) estimate \geq 60 mL/min.

Basis for setting

It is expected that radiotherapy will enhance the efficacy of anti-tumor immunity. We speculate that the use of nivolumab in combination with post-irradiation therapy may induce an abscopal effect in some cases. We decided to start nivolumab between Days 15-22, with Day 1 as the start date of radiotherapy. Because IFN- γ and TNF- α in serum increased about 10-14 days after irradiation (mouse model) (4), and immune responses such as CTL activation were observed about 2 weeks after administration of peptide vaccines and activated dendritic cells (clinical observation).

A possible disadvantage of this treatment strategy is that the combination of radiotherapy and nivolumab may increase or intensify adverse events; however, as far as we have searched, there have been no reports of serious adverse events occurring.

2.4. Combination therapy

1) Acceptable concomitant and supportive therapies

The following concomitant and supportive care may be given as necessary. However, the name of the applicable event, the name of the drug used, its dosage, and the duration of use, etc., should be noted in the case report form. The drugs listed in this section are examples and do not limit the drugs used.

- ① Symptomatic treatment of Grade 1 or less interstitial lung disease and eye disorders caused by nivolumab or that of Grade 2 or less bronchospasm, diarrhea, colitis, neurotoxicity, hypersensitivity reactions, injection reactions (fever, chills, nausea, pain, headache, cough, scratchiness, rash, etc.) and thrombocytopenia. The dosage and administration of each drug used is in accordance with the package insert (insurance indications).
- ② Hepatoprotective drugs for the following liver function abnormalities caused by nivolumab. AST or ALT < 5–10 times the upper limit of the facility reference value for more than 2 weeks. AST or ALT < 10 times the upper limit of the facility reference value. Total bilirubin level < five times the upper limit of the facility reference value. Concomitant AST or ALT < three times the upper limit of the facility reference value and total bilirubin < two times the upper limit of the facility reference value. The dosage and administration of the respective drug should be in accordance with the accompanying documentation (insurance coverage).
- ③ Nausea, vomiting and anorexia (hostility) caused by radiotherapy. Metoclopramide (primperan) is tolerated to prevent symptom exacerbation. The standard of care for use is nausea, vomiting or anorexia of Grade 2 or above. The dosage and administration of metoclopramide (primperan) to be used should be in accordance with the package insert (insurance indication).
- ④ Radiotherapy-induced dermatitis.
The use of skin protectants such as hydride for Grade 1 dermatitis and topical corticosteroids for Grade 2 or higher skin rashes is acceptable. The dosage and administration of each drug should be in accordance with the package insert (insurance coverage).
- ⑤ Radiotherapy to other metastatic lesions.
During the course of nivolumab treatment, if palliative radiotherapy becomes necessary due to symptoms such as pain and bleeding worsen caused by an increase in lesions other than those treated with radiotherapy, radiotherapy should be allowed and observation continued if there are other evaluable lesions with no history of radiotherapy.

2) Unacceptable concomitant and supportive therapies

During protocol treatment (from the start of radiotherapy until after the sixth dose of nivolumab), none of the following treatments should be administered. Any of the following treatments are considered a protocol deviation.

- ① Treatment for cancers other than this protocol (chemotherapy, surgery, radiotherapy, endocrine therapy, immunotherapy, etc.). However, radiotherapy is permitted if the provisions of 2.4.1.⑤ are met.
- ② Other treatments presumed to influence the assessment of efficacy and safety in the study.
- ③ Immunosuppressive therapy. However, corticosteroids are only allowed in doses of hydrocortisone \leq 200 mg/day for transfusion allergy and small-dose steroids (< 15 mg/day of prednisone) for the prevention of cerebral hypertension symptoms and adrenal insufficiency.
- ④ Administration of other study medicines, including development products.

2.5. Criteria for changes in dosage/use

1) Radiation dose escalation and dose reductions will not be performed. Nivolumab dosage and administration should be in accordance with the recommendations for the treatment of unresectable advanced or recurrent gastric cancer (Appendix).

2) Criteria for discontinuation of treatment

- ① Nivolumab (anti-PD-1 Ab) discontinuation criteria:
 - 1) Failure to meet the criteria for initiation of nivolumab (anti-PD-1 Ab) in '2.3.(2) Nivolumab (anti-PD-1 Ab) treatment' and failure to resume treatment within 14 days of the planned treatment date.
 - 2) If a patient requests discontinuation of nivolumab treatment, irrespective of whether or not it is associated with an adverse event.
 - 3) Death during protocol treatment.
 - 4) Ineligibility due to a known protocol violation, change of pathology diagnosis after enrolment, etc.
 - 5) It is deemed inappropriate to continue treatment due to apparent worsening of clinical symptoms caused by disease progression.
 - 6) Occurrence of Grade 2 or higher interstitial lung disease.
 - 7) Occurrence of Grade 2 or higher eye disorders.
 - 8) Occurrence of Grade 3 or higher bronchospasm, diarrhea, colitis, neurotoxicity, hypersensitivity reactions and injection reactions.
 - 9) Occurrence of Grade 3 or higher thrombocytopenia.
 - 10) Abnormalities in liver function that fulfill one of the following criteria have emerged. AST or ALT $> 5-10$ times the upper limit of the facility reference value for more than 2 weeks.

AST or ALT > 10 times the upper limit of the facility reference value. Total bilirubin levels > 5 times the upper limit of the institutional reference value. Concurrent AST or ALT > 3 times the upper limit of the facility reference value and total bilirubin > 2 times the upper limit of the facility reference value.

11) The principal investigator or a member of research team decides that continued treatment with nivolumab is not appropriate.

② Criteria for discontinuation of radiotherapy

Discontinue radiotherapy if any of the following occur:

- 1) Failure to meet the treatment criteria for radiotherapy in '2.3(2) – Radiotherapy'.
- 2) When the attending doctor decides that discontinuation is necessary due to an adverse event.
- 3) If the patient requests discontinuation of radiotherapy, irrespective of whether or not it is associated with an adverse event.
- 4) Patient deaths.
- 5) Ineligibility due to a known protocol violation, change of pathology diagnosis after enrolment, etc.
- 6) The principal investigator or a member of research team decides that continuation of treatment is not appropriate, taking into account efficacy or safety.

If this protocol treatment is discontinued, follow the decision of the attending doctor with regard to subsequent treatment. The reasons for discontinuation should be documented in the medical record and the case report form. If consent is withdrawn after treatment has started, it should be made as clear as possible whether the withdrawal of consent was due to ineffectiveness of the treatment or to an adverse or incidental event, and this should be record in order to assist in the selection of the case for safety evaluation. If circumstances permit, a discontinuation inspection should be carried out within 14 days of the decision to discontinue (see 2.7.).

2.6. Evaluation items

The primary endpoint of this clinical trial is the disease control rate of non-irradiated target lesions, in order to explore the efficacy (additive effect) of radiotherapy to immunotherapy with nivolumab, which is already established as third-line chemotherapy in unresectable advanced or recurrent gastric cancer. Secondary endpoints will also include 1) median survival time (MST) and 2) safety (grade and frequency of adverse events), 3) local control rate (disease control rate of irradiated target lesions), and 4) immunological parameters.

(1) Primary endpoint

Disease control rate

The rate of patients with a best overall response of stable disease (SD) or better confirmed by 180 days, starting from the start date of radiotherapy (Day 1). CT (MRI is also acceptable) and whole-body PET-CT will be used to determine overall response such as complete response (CR), partial response (PR), SD, progressive disease (PD) at each imaging time according to the RECIST Guidelines Version 1.1. If imaging is not available, the patient is considered deficient (NE). CR or PR as the best overall response is defined as two or more consecutive CRs or PRs. If the best overall response does not meet the criteria for CR or PR, and the patient has no PD on the 6th dose of nivolumab and Day 120, the best overall response is considered to be SD. For evaluation, target lesions other than those treated with local radiotherapy are considered as target lesions. If the lesions cannot be evaluated based on the above criteria, they will not be included in the analysis for best overall response.

(2) Secondary endpoint

1) Median survival time (MST)

Overall survival is defined as the period from the start date of radiotherapy until the date of death from any cause. In surviving cases, the last date of confirmation of survival is the date of termination (survival confirmed by telephone contact is acceptable, but confirmation of survival should be recorded in the medical record). Untraceable cases are terminated on the last date of confirmed survival before the loss of follow-up. At the end of the study period, all enrolled cases will be confirmed alive.

2) Safety (grade and frequency of adverse events)

The frequency of adverse events occurring from the start date of radiotherapy to the end of study will be tabulated by adverse event name and worst grade according to CTCAE ver.4.0. All adverse events are summarized without regard to causal relationships to the study treatment. A serious adverse event is defined as having occurred if at least one of the following adverse events is observed, and the frequency and proportion of serious adverse events is calculated.

- ① Death during protocol treatment or within 30 days of last protocol treatment.
- ② Death with undeniable causal relationship to protocol treatment after 31 days of last protocol treatment.
- ③ Grade 4 infection with neutropenia.
- ④ Grade 4 non-hematological toxicity (excluding adverse events in the blood/bone marrow).

3) Local control rate

The rate of patients with a best overall response of SD or better confirmed by 180 days, starting from the start date of radiotherapy (Day 1). CT (MRI is also acceptable) and whole-body PET-CT will be used to determine overall response such as complete response (CR), partial response (PR), SD, progressive disease (PD) at each imaging time according to the RECIST Guidelines Version 1.1. If imaging is not available, the patient is considered deficient (NE). CR or PR as the best overall response is defined as two or more consecutive CRs or PRs. If the best overall response does not meet the criteria for CR or PR, and the patient has no PD on the 6th dose of nivolumab and Day 120, the best overall response is considered to be SD. For evaluation, target lesions are tumors that are treated with local radiotherapy. If the lesions cannot be evaluated based on the above criteria, they will not be included in the analysis for best overall response.

4) Immunological parameters

Histological examination

- Analysis of the tumor microenvironment by immunohistochemistry.
 - * Immunohistochemistry will be performed in cases with available biopsy and/or resected surgical specimens.

Peripheral blood test

- Analysis of peripheral blood lymphocyte subset
- Measurement of cytokines in plasma
- Analysis of regulatory T cell and antigen-specific T cell function
 - * According to advance of immunological technique, the contents of immunological parameter analyses, such as antigen-specific T cell function analysis, highly multiplexed flow cytometric analysis, T cell receptor repertoire analysis, and assessment of tumor mutation burden using plasma derived ctDNA, will also be evaluated.
 - * These analysis will be performed relating to clinical outcomes, such as two groups divided with MST.

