- 5) Blood biochemistry: total protein, albumin, total bilirubin, direct bilirubin, AST, ALT, ALP, γ -GTP, BUN, creatinine, LDH, uric acid, CPK, P, Ca, Na, K, Cl, CRP, blood glucose.
- 6) Presence of adverse events (CTCAE v4.0 Japanese translation).
- 7) Immunological parameters.

During nivolumab administration

(After the second dose, assess the following items on the day of administration or the day before administration. Assess following items once from 7 days before to 7 days after the imaging examination date.)

- 1) General findings (temperature, blood pressure, pulse).
- 2) General condition: PS (ECOG).
- 3) Subjective and objective symptoms: fever, nausea, vomiting, diarrhea, decreased appetite, etc. (to be confirmed according to CTCAE v4.0 Japanese translation).
- 4) Blood count (peripheral blood): white blood cell count and fractions, red blood cell count, hemoglobin, MCV, MCH, MCHC, Ht, platelets.
- 5) Blood biochemistry: total protein, albumin, total bilirubin, direct bilirubin, AST, ALT, ALP, γ -GTP, BUN, creatinine, LDH, uric acid, CPK, P, Ca, Na, K, Cl, CRP, blood sugar.
(The following items are only available at the third and sixth doses) RA, ANA, SP-D, KL-6, TSH, free T3, free T4, tumor markers (CEA, CA19-9).
- 6) Contrast-enhanced CT of the chest, abdomen and pelvis (at third and sixth doses). PET-CT is also acceptable. Add MRI if necessary.
- 7) Presence or absence of PD (diagnosed comprehensively based on imaging and clinical findings).
- 8) Presence or absence of adverse events (CTCAE v4.0 Japanese translation).
- 9) Immunological parameters.

During observation

(Assess following items once from 14 days before to 14 days after the 3rd and 6th dose of Nivolumab and Day120.)

- 1) Contrast-enhanced CT of chest, abdomen and pelvis. PET-CT is also acceptable. Add MRI if necessary.

After completion of the protocol

(Assess following items once from 14 days before to 14 days after the Day180.)

- 1) General findings (temperature, blood pressure, pulse).
- 2) General condition: PS (ECOG).
- 3) Subjective and objective symptoms: fever, nausea, vomiting, diarrhea, decreased appetite, etc. (to be confirmed according to CTCAE v4.0 Japanese translation).
- 4) Blood count (peripheral blood): white blood cell count and fractions, red blood cell count, hemoglobin, MCV, MCH, MCHC, Ht, platelets.

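### The stable-disease rule omits the third-dose scan and ties SD to a sixth nivolumab dose, so non-responders can be misclassified in either direction

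*Protocol*

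**What the plan says.** **Best response.** Protocol section 2.6 has response read as CR, PR, SD or "progressive disease (PD) at each imaging time according to the RECIST Guidelines Version 1.1". Separate sentences turn these reads into a best overall response.

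- Response: "CR or PR as the best overall response is defined as two or more consecutive CRs or PRs".
- Stable disease, when the response rule is not met: "the patient has no PD on the 6th dose of nivolumab and Day 120, the best overall response is considered to be SD".
- Not evaluable: missing imaging is recorded as NE, and "If the lesions cannot be evaluated based on the above criteria, they will not be included in the analysis for best overall response".

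No sentence says when the best overall response is PD. The local control rate uses the same text, applied to the irradiated lesions.

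**Scans.** Section 2.7 schedules imaging "from 14 days before to 14 days after the 3rd and 6th dose of Nivolumab and Day120", and again at Day 180 and at cessation of treatment.

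**Stopping.** The progression-related criterion for stopping nivolumab in section 2.5 is: "It is deemed inappropriate to continue treatment due to apparent worsening of clinical symptoms caused by disease progression". PD on imaging alone is not listed. Patient request, toxicity, a delay that cannot be resolved and the investigator's judgement are separate routes.

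**Analysis.** Section 2.10 analyses the FAS and divides patients with CR, PR or SD by the number of eligible patients. SAP sections 6.1 and 6.2.2 refer to SD or better by Day 180 and give no rule by time point. SAP section 6.5 plans no sensitivity analysis for missing values.

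**The concern.** Every patient without a confirmed response depends on the SD sentence for a place in the numerator. It has two gaps.

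- **Early progression.** The third-dose scan is scheduled but is not part of the SD condition. Because imaging PD alone does not end nivolumab, a patient with PD at dose three can reach dose six and Day 120. If both of those scans are read as non-PD, the written condition for SD is met.
- **Early stopping without PD.** The sixth dose is a treatment event, not a calendar date. A non-responder who stops for toxicity or by choice has no sixth-dose assessment. With a clean Day 120 scan, the patient could be called SD, not controlled or not evaluable. Section 2.6 points towards leaving the patient out, whereas section 2.10 points towards keeping the patient in the denominator.

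The first gap can raise the reported rate. The second can lower it, or raise it if uncontrolled patients are the ones left out. At stake is whether the trial's main result is read as better than 40%.

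**Working it through.** **Inputs.** Section 2.8 gives a reference rate of 40%, an improvement of 20 points (read as 60%), one-sided 5%, power 80%, 39 required and 40 planned. Section 2.10 and SAP section 6.1 give a two-sided 90% Clopper-Pearson interval. Section 2.1 starts nivolumab between Days 15 and 22, every two weeks, six doses.

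**1. The plan's sample size.** The arcsine formula gives n = [(1.645 + 0.842) / (2 × (asin √0.6 − asin √0.4))]² = 38.1, so 39. This matches the protocol and is not in dispute.

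**2. Timing on schedule.** Dose k falls on start + 14 × (k − 1) days. Dose three is Day 15 + 28 = 43 to Day 22 + 28 = 50. Dose six is Day 15 + 70 = 85 to Day 22 + 70 = 92. The scan left out of the SD rule therefore comes 42 days before the first scan that the rule uses.

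**3. Cut-off.** The documents state no decision rule. The one-sided 5% level in section 2.8 corresponds to the lower limit of a two-sided 90% interval lying above 40%. At n = 40:

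- 22 controlled: lower limit 40.9%, above 40%
- 21 controlled: lower limit 38.5%, below 40%

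So 22 is the smallest count that succeeds. P(X ≥ 22) for Binomial(40, 0.40) is 3.9%, and for Binomial(40, 0.60) it is 79.1%.

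**4. Early PD counted as SD, true rate 40%.** If on average k of 40 patients are affected, the counted rate is 0.40 + k/40. The documents give no value for k, so k is assumed.

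| k per 40 | Counted rate | P(X ≥ 22) |
|---|---|---|
| 0 | 40.0% | 3.9% |
| 1 | 42.5% | 7.6% |
| 2 | 45.0% | 13.3% |
| 4 | 50.0% | 31.8% |

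**5. Stable early stoppers counted as not controlled, true rate 60%.** The denominator stays at 40 and the counted rate is 0.60 − k/40, with k again assumed.

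| k per 40 | Counted rate | P(X ≥ 22) |
|---|---|---|
| 0 | 60.0% | 79.1% |
| 2 | 55.0% | 56.5% |
| 4 | 50.0% | 31.8% |

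**6. Denominator.** Suppose 24 of 40 are truly controlled and two of the 24 are stable patients who stopped early. Counted as SD, the rate is 24/40 = 60.0%. Counted as not controlled, it is 22/40 = 55.0%. Left out, it is 22/38 = 57.9%. If the patients left out are uncontrolled, the estimate moves up: 16/40 = 40.0% becomes 16/38 = 42.1%, 16/36 = 44.4% or 16/32 = 50.0% when 2, 4 or 8 are dropped.

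**The case against.** The strongest reply is that section 2.6 requires RECIST 1.1 at each imaging time, and section 2.7 has the presence or absence of PD recorded during nivolumab. An analyst could therefore count PD at dose three as progression. A reader might infer that third-dose PD simply does not count, but the documents do not go that far: the rule is silent, and PD that persists at dose six or Day 120 still blocks SD. What stands is that the requirement covers the individual reads, while the only sentence that turns reads into SD names two looks. Two analysts could classify the same patient differently.

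A reader might also infer that patients who never reach dose six cannot be classified at all. That is too broad. They can be CR or PR on two consecutive scans, and PD can be recorded at dose three, at cessation or at Day 120. It could even be argued that a patient with no sixth dose has no PD at it. Only SD for non-responders is undefined, together with their place in the denominator.

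The size is open to challenge too. The values of k have no source in the documents. At a true 40%, k = 4 is one in six of the 24 uncontrolled patients, and each would need PD at dose three followed by non-PD at both later looks. The cut-off of 22 is inferred, since the analysis sections specify only a rate with an interval and describe the aim as exploratory. These points limit how firmly the size can be stated. They do not remove the ambiguity.

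**Conclusion.** The concern holds in this form: the SD rule omits a scheduled scan and makes SD depend on a sixth dose, the SAP does not repair either gap, and the exclusion in section 2.6 conflicts with the denominator in section 2.10. Local control inherits the same fault.

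The direction of the net error cannot be known in advance. Under the assumed rates, the chance of a false success at a true 40% could be 7.6% to 31.8% instead of 3.9%, and the chance of success at a true 60% could be 56.5% or 31.8% instead of 79.1%. These figures rest on the inferred cut-off of 22 of 40 and show sensitivity only; they do not forecast how many patients will be affected.

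A reader might also infer that one scan could serve as both the sixth-dose and the Day 120 look. The documents do not support making that a finding. On schedule the two windows share only Day 106 (92 + 14 and 120 − 14), and only when nivolumab starts on Day 22. Delays would widen the overlap, but section 2.7 lists the two looks separately and nothing allows a scan to be counted twice.

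**What to change.** Replace the SD sentence in protocol section 2.6 and put the same algorithm in SAP sections 6.1 and 6.2.2:

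1. A patient who meets the existing confirmed CR or PR rule is classified as CR or PR.
2. Otherwise, SD requires no PD at any scheduled or cessation assessment up to and including the Day 120 window, and an evaluable scan in that window, regardless of the number of nivolumab doses received.
3. A treated eligible patient who meets neither rule stays in the denominator as not controlled. This covers PD, death before the Day 120 scan and no evaluable Day 120 scan. The exclusion sentence in section 2.6 is amended to agree with the denominator in section 2.10.

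Apply the same rule to local control.

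The cost is a few lines of text. The scans are already scheduled, SAP section 8.7 already lists examination dates and tumour diameters, and no treatment changes. The downside is that the reported rate may be slightly lower, because early PD and missing Day 120 scans count against control.
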